5.2 Treatment Dosage and Administration

Subjects in this trial will be administered entinostat, 5mg PO, once weekly (D1, D8, D15 of a 21-day cycle) starting on day 1 of study treatment. Pembrolizumab, 200 mg will be administered intravenously (IV) every 3 weeks and initiated at cycle 2 after the mandatory research tumor biopsy in the end of cycle 1, beginning of cycle 2 (day 22±2 days). Combination therapy with both agents will continue if subject is receiving clinical benefit from therapy for up to 27 weeks (8 cycles of combination therapy or approximately 6 months). Study therapy will be discontinued for intolerable toxicity, disease progression or for other reasons at the discretion of the investigator.

Agent	Required Premedications; Precautions	Dose	Route	Schedule	Cycle Length
Entinostat	Take on an empty stomach i.e., at least 2 hours after a meal and at least 1 hour before the next meal.	5 mg ³	Oral (PO)	Start on study D1 of cycle 1 and administer once weekly (i.e., D1, D8, D15 of each cycle) for 9 cycles qwk) (±1 day)	Every 21* days
Pembrolizumab	Risk for immune-mediated ¹ and infusion-related ² reactions	200 mg ³	IV; administer over 30 min (range -5, +10 min)	Start on study D22 (± 2 days) of the study (i.e., D1 of cycle 2) and administer every 21 (± 2) days (q3wk) x 8 cycles (i.e., cycles 2-9)	

1. See Section 5.3.2 for management guidelines for immune-mediated AEs.
2. See Section 5.6.1 for management guidelines for infusion-related AEs
3. On days when entinostat is administered on the same day as pembrolizumab, entinostat should be taken before the pembrolizumab infusion.

*Entinostat monotherapy for cycle 1 and combination therapy should be initiated on D1 of cycle 2 and continue until withdrawal for toxicity, withdrawal for patient preference, disease progression or the subject completes 27 weeks of protocol-directed therapy. Entinostat cannot be continued beyond the 27-week duration of study-directed therapy for the trial, irrespective of treatment response.

*Pembrolizumab will be started on D22 of the study (i.e., D1 of cycle 2) and may continue for up to 24 weeks in combination with entinostat (i.e. cycles 2-9). Following completion of the trial therapy at 27 weeks and on condition that there is no disease progression, pembrolizumab can be continued per investigator discretion, as per standard of care guidelines.

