5.3.1 Entinostat Dosing Modification Guidelines

All dose modifications should be based on the AEs requiring the greatest modification and also meet criteria for dose adjustment. AEs should be properly documented in source documents. Investigators may take a more conservative approach than the guidelines outlined below based on clinical judgment that is in the best interest of the subject.

Management of toxicities that are at least possibly related to entinostat, with toxicities graded by the Investigator according to the NCI, CTCAE, version 5.0 should be managed as follows:

Non-hematologic Toxicity	
Toxicity	Dose Modifications for Entinostat
Grade 4	Administer symptomatic remedies/start prophylaxis. Hold dose until recovery to Grade 1 or baseline under the following directions: 
 1. If recovered within 4 weeks of onset (i.e.: ≤ 3 missed doses), resume study drug as follows: 
 • If receiving 5 mg, restart study drug at 3 mg, • If receiving 3 mg, restart study drug at 2 mg, • If receiving 2 mg, discontinue study treatment. 2. If not recovered within 4 weeks, permanently discontinue study drug.

Non-hematologic Toxicity	
Toxicity	Dose Modifications for Entinostat
Grade 3	Administer symptomatic remedies/ start prophylaxis. Hold dose until recovery to Grade 1 or baseline under the following directions: 
 1) If recovered within 1 week, resume study drug at prior dose. If not recovered within 1 week, continue to hold dose. 2) If recovered within 2-4 weeks, resume study drug as follows: 
 • If receiving 5 mg, restart study drug at 3 mg, • If receiving 3 mg, restart study drug at 2 mg, • If receiving 2 mg, permanently discontinue study drug. 3) If not recovered within 4 weeks, permanently discontinue study drug.

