Recurrence of the same \geq Grade 3 toxicity, despite dose reduction	If the same \geq Grade 3 event recurs : 
 1) Administer symptomatic remedies/ start prophylaxis. Hold¹ dose until recovery to Grade 1 or baseline. 2) If recovered within 2 weeks, resume study drug as follows: 
 a. If receiving 5 mg, restart study drug at 3 mg, b. If receiving 3 mg, restart study drug at 2 mg, c. If receiving 2 mg, permanently discontinue study drug. 3) If the same \geq Grade 3 event recurs (i.e., third occurrence) despite entinostat dose reduction to 2 mg, as described above, discontinue study drug.
\leq Grade 2	Administer symptomatic remedies/start prophylaxis. Dosing of study drug may be interrupted at the Investigator's discretion. 
 • If dose is held for 4 consecutive weeks, permanently discontinue study drug¹. • If toxicity resolves, resume entinostat at the original dose.

If greater than 50% of doses are missed during any 6-week period, discontinue from study drug treatment. Entinostat must also be discontinued in case of permanent discontinuation of pembrolizumab.

Hematologic Toxicity	
Toxicity	Dose Modifications for Entinostat
\geq Grade 3 neutropenia, \geq Grade 3 uncomplicated thrombocytopenia, or Grade 2 complicated thrombocytopenia	Administer symptomatic remedies/start prophylaxis. Hold dose ¹ until recovery to Grade 1 or study baseline under the following direction: 
 1) If not recovered by next scheduled dose, skip the dose. If recovered by next scheduled dose, resume study drug at prior dose. 2) If receiving 2 mg dose, and not recovered by either of the next two scheduled doses, permanently discontinue study treatment. Otherwise, skip each dose. If recovered for either of these doses, resume study drug as follows: 
 a. If receiving 5 mg, restart study drug at 3 mg, b. If receiving 3 mg, restart study drug at 2 mg. 3) If not recovered within 4 weeks, permanently discontinue study drug.

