Dosing interruptions are permitted in the case of medical/surgical events or logistical reasons not related to study therapy (e.g., elective surgery, radiation therapy, unrelated medical events, patient vacation, and/or holidays). Subjects should be placed back on study therapy within 3 weeks (i.e., 21 days) of the scheduled interruption, unless otherwise discussed with the Sponsor. The reason for interruption should be documented in the patient's study record. If pembrolizumab is permanently discontinued, entinostat must be discontinued as well.

Attribution of Toxicity:

When study interventions are administered in combination, attribution of an adverse event to a single component is likely to be difficult. Therefore, while the investigator may attribute a toxicity event to the combination, to entinostat alone or to pembrolizumab alone], for adverse events listed in the table below, both interventions must be held according to the criteria in the table below: Dose Modification and Toxicity Management Guidelines for Immune-Related Adverse Events Associated with Pembrolizumab and IO Combinations.

Holding Study Interventions:

When study interventions are administered in combination, if the AE is considered immune-related, both interventions should be held according to recommended dose modifications.

Restarting Study Interventions:

Participants may not have any dose modifications (no change in dose or schedule) of pembrolizumab in this study, as described in the table below.

- If the toxicity does not resolve or the criteria for resuming treatment are not met, the participant must be discontinued from all study interventions.
- If the toxicities do resolve and conditions are aligned with what is defined in the table below, the combination of entinostat and pembrolizumab may be restarted at the discretion of the investigator. In these cases where the toxicity is attributed to the combination or to entinostat alone, re-initiation of pembrolizumab as a monotherapy may be considered at the principal investigator's discretion.

Dose modification and toxicity management guidelines for immune-related AEs associated with pembrolizumab monotherapy and IO Combinations

General instructions:

1. Severe and life-threatening irAEs should be treated with IV corticosteroids followed by oral steroids. Other immunosuppressive treatment should begin if the irAEs are not controlled by corticosteroids.

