2. Study intervention must be permanently discontinued if the irAE does not resolve or the corticosteroid dose is not ≤ 10 mg/day within 12 weeks of the last study intervention treatment.
3. The corticosteroid taper should begin when the irAE is \leq Grade 1 and continue at least 4 weeks.
4. If study intervention has been withheld, study intervention may resume after the irAE decreased to \leq Grade 1 after corticosteroid taper.

irAEs	Toxicity Grade (CTCAE v5.0)	Action With Pembrolizumab	Corticosteroid and/or Other Therapies	Monitoring and Follow-up
Pneumonitis	Grade 2	Withhold	
 • Administer corticosteroids (initial dose of 1 to 2 mg/kg prednisone or equivalent) followed by taper • Add prophylactic antibiotics for opportunistic infections 	
 • Monitor participants for signs and symptoms of pneumonitis • Evaluate participants with suspected pneumonitis with radiographic imaging and initiate corticosteroid treatment
	Recurrent Grade 2, Grade 3 or 4	Permanently discontinue		

irAEs	Toxicity Grade (CTCAE v5.0)	Action With Pembrolizumab	Corticosteroid and/or Other Therapies	Monitoring and Follow-up
Diarrhea/Colitis	Grade 2 or 3	Withhold	
 Administer corticosteroids (initial dose of 1 to 2 mg/kg prednisone or equivalent) followed by taper 	
 Monitor participants for signs and symptoms of enterocolitis (ie, diarrhea, abdominal pain, blood or mucus in stool with or without fever) and of bowel perforation (ie, peritoneal signs and ileus) Participants with \geqGrade 2 diarrhea suspecting colitis should consider GI consultation and performing endoscopy to rule out colitis Participants with diarrhea/colitis should be advised to drink liberal quantities of clear fluids. If sufficient oral fluid intake is not feasible, fluid and electrolytes should be substituted via IV infusion
	Recurrent Grade 3 or Grade 4	Permanently discontinue		
AST or ALT Elevation or Increased Bilirubin	Grade 2 ^a	Withhold	
 Administer corticosteroids (initial dose of 0.5 to 1 mg/kg prednisone or equivalent) followed by taper 	
 Monitor with liver function tests (consider weekly or more frequently until liver enzyme value returned to baseline or is stable)

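### For a steroid-tapered immune-related event possibly related to entinostat, Section 5.3.2 permits restart of the combination when the Section 5.3.1 missed-dose rule has normally already ended entinostat

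*Combined protocol and SAP*

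**What the plan says.** **Section 5.3.1 (entinostat).** After the non-hematologic table, and again after the hematologic table, the protocol states: "If greater than 50% of doses are missed during any 6-week period, discontinue from study drug treatment". Neither copy mentions irAEs or attribution. The non-hematologic row for Grade 2 or lower adds a second limit: four consecutive weeks of held dosing means permanent discontinuation. Doses skipped during a toxicity hold are counted as missed. In the Grade 4 row, the condition "If recovered within 4 weeks of onset" is explained in brackets as no more than "3 missed doses), resume study drug as follows". The section is introduced as covering toxicities with at least a possible relation to entinostat.

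**Section 5.3.2 (irAEs on pembrolizumab and the combination).** Whatever drug the investigator blames, for events in the table "both interventions must be held according to the criteria in the table below". The general instructions then set the timing:

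- "The corticosteroid taper should begin when the irAE is" Grade 1 or lower, and the taper lasts at least 4 weeks.
- "If study intervention has been withheld, study intervention may resume after the irAE decreased to" Grade 1 or lower, after the taper.
- Permanent discontinuation is required only if, within 12 weeks of the last treatment, the event has not resolved or the steroid dose is still above 10 mg/day.

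If the event resolves as the table requires, "the combination of entinostat and pembrolizumab may be restarted at the discretion of the investigator". Where the toxicity is attributed to the combination or to entinostat alone, restarting pembrolizumab by itself is offered as a further option.

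**Section 5.3.3** lists AST/ALT elevation and diarrhea among the toxicities that the two drugs share. For Grade 3 or higher events attributed equally to both, it sends the reader to 5.3.1 and 5.3.2 together.

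**The concern.** Entinostat is given once a week, so a hold that must include a taper of at least 4 weeks uses up most of a 6-week period. The section that authorizes the restart does not mention the missed-dose limit, and the section that sets the limit does not mention the restart. A site managing, for example, Grade 2 transaminase elevation judged possibly related to both drugs would find permission to restart the combination in one place and an instruction to discontinue entinostat in the other.

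The first stake is patient safety: the documents give opposite instructions on re-exposing a patient to entinostat after an irAE. The second is interpretation. The toxicity and 27-week PFS results are meant to describe the combination, and two patients with the same event could receive different combination exposure because of how the text was read.

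**Working it through.** **Inputs**

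- One entinostat dose every 7 days, so 6 scheduled doses in 6 weeks (5.2).
- Stopping threshold: more than 50% of 6, that is, 4 or more missed (5.3.1).
- Length of hold: L = R + T, where R is the time to reach Grade 1 or lower and T is the taper, at least 28 days (5.3.2).
- A missed dose may be taken up to 48 hours late (6.1.3).

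**Count.** Put the last dose taken at day 0, so doses fall due on days 7, 14, 21, 28 and so on. Let the hold start at day s, with s between 0 and 7. Without the late-dose allowance, a dose due on day d is missed if s ≤ d < s + L.

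**The plan's own figure.** A hold that starts just after a dose and ends just before day 28 misses days 7, 14 and 21. That is 3 doses, which reproduces the bracketed figure in 5.3.1. It is the best case: a hold of 27.4 days that starts on day 1 ends at day 28.4 and misses 4.

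**irAE hold with the minimum taper of 28 days, no late-dose allowance**

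| R (days) | L (days) | Missed in a 6-week period | Share |
|---|---|---|---|
| 0 | 28 | 4 of 6 | 4/6 = 67% |
| 7 | 35 | 5 of 6 | 5/6 = 83% |
| 14 | 42 | 6 of 6 | 6/6 = 100% |

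These counts do not depend on s, because any 28-day span contains exactly four weekly due dates. All exceed 50%.

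**With the 48-hour allowance.** A dose is now missed only if s + L > d + 2. The day-28 dose is saved if s + R + 28 ≤ 30, that is, if s + R ≤ 2. The count is then 3 of 6 (50%), which is not above the limit. This needs a hold that starts within about 2 days of a dose, almost immediate recovery, a taper of exactly 28 days and a late next dose. Otherwise the threshold is still passed: 4 to 5 of 6 (67% to 83%) at R = 7, and 5 to 6 of 6 (83% to 100%) at R = 14.

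**Four-consecutive-week row.** For a Grade 2 or lower event within the scope of 5.3.1, L ≥ 28 days reaches that limit as well.

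**Which events.** The conflict needs a table event that is withheld rather than permanently discontinued, and that is treated with a taper. Examples are Grade 2 pneumonitis, Grade 2 or 3 diarrhea/colitis, and Grade 2 liver enzyme elevation or nephritis, when at least possibly related to entinostat. Where the table already requires permanent discontinuation (for example Grade 3 or 4 pneumonitis) there is no restart to conflict with. Events managed without a taper, such as type 1 diabetes treated with insulin, can have shorter holds.

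**Timing against the endpoints.** The primary endpoint uses the day-22 biopsy, taken before pembrolizumab. Response is first assessed on day 64. For a hold of at least 28 days to have ended by then, it must begin by day 64 − 28 = 36, which is 14 days after pembrolizumab starts. Early response is therefore little affected; toxicity and 27-week PFS are more exposed.

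**The case against.** The strongest answer is that attribution already selects the section. 5.3.1 opens by limiting itself to toxicities at least possibly related to entinostat, and both copies of the missed-dose sentence sit under its tables. Section 5.6 applies its steroid guidance to events that the investigator relates to pembrolizumab, sends entinostat-related diarrhea and transaminitis back to 5.3.1, and says that autoimmune interstitial nephritis occurs with pembrolizumab but not with entinostat.

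Part of this stands. A reader might infer that every irAE in the 5.3.2 table meets the contradiction. The documents do not support that: for an event attributed to pembrolizumab alone, the section's scope points one way and the unqualified missed-dose sentence the other, so the position is unclear rather than contradictory. The objection does not cover events possibly related to both drugs. 5.3.2 calls single-drug attribution difficult, holds both drugs regardless, and writes its restart text to include events attributed to the combination or to entinostat alone. 5.3.3 names both sections together for jointly attributed events of Grade 3 or higher.

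It can also be said that the restart is only permissive, so the stricter rule prevails. No sentence says so. The 5.3.1 instruction to follow the event that needs the greatest modification ranks adverse events, not sections. On that reading the permission to restart would be almost empty for steroid-tapered events within the scope of 5.3.1.

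Finally, the 10 mg/day wording might suggest resuming before the taper ends. That wording is a trigger for discontinuation; the separate instruction on resumption places it after the taper.

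**Conclusion.** The conflict is real for irAEs in the 5.3.2 table that are treated with a steroid taper and judged at least possibly related to entinostat, including those attributed to the combination. By the time 5.3.2 permits restart, 4 or more of 6 weekly doses (at least 67%) have normally been missed, against a limit of 3 of 6. For events attributed to pembrolizumab alone, the applicable rule is unclear. Events without a taper and the 48-hour edge case are exceptions.

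This rests on three readings: held doses count as missed, as the 5.3.1 bracket implies; study drug in 5.3.1 means entinostat, as its 5, 3 and 2 mg steps imply; and resumption after the taper means after its end.

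Two stronger inferences should be resisted. A reader might suppose that patients would leave or be reassigned in the response or PFS analysis, each shifting a 10-patient rate by 10 percentage points. No rule does this: evaluability is settled by day 22 (9.1.1), and stopping entinostat removes nobody from either analysis. A reader might also estimate how often the conflict will arise from the pembrolizumab monotherapy rates in 1.5.2. Those are any-grade rates over a median follow-up of 15 to 21 months, and they include events that would be permanently discontinued here anyway. In this trial pembrolizumab lasts up to 24 weeks and entinostat cannot pass week 27, while Section 6.2.4 gives median onset of 5 months for pneumonitis and 6.5 months for colitis. The documents do not give a usable frequency.

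**What to change.** Reconcile 5.3.1 and 5.3.2. The protocol should state:

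- whether doses held under the 5.3.2 table count toward the limit of more than 50% missed in 6 weeks and toward the four-consecutive-week limit;
- whether the answer depends on attribution, including attribution to pembrolizumab alone.

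The restart sentence in 5.3.2 should then be made to agree. Which rule governs is for the sponsor to decide; this review takes no position.

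The report should say which patients resumed the combination and which resumed pembrolizumab alone, so that the toxicity and 27-week PFS results can be read with actual exposure in view. The dosing diary and accountability records in 6.1.4 and 6.1.5 already capture missed entinostat doses, amounts and dates, so no new eCRF field is needed.

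The cost is one or two sentences in the next amendment, with no extra patients or procedures.

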Myocarditis	Grade 1	Withhold	
 Based on severity of AE administer corticosteroids 	
 Ensure adequate evaluation to confirm etiology and/or exclude other causes
	Grade 2, 3 or 4	Permanently discontinue		
Exfoliative Dermatologic Conditions	Suspected SJS, TEN, or DRESS	Withhold	
 Based on severity of AE administer corticosteroids 	
 Ensure adequate evaluation to confirm etiology or exclude other causes
	Confirmed SJS, TEN, or DRESS	Permanently discontinue		
All Other irAEs	Persistent Grade 2	Withhold	
 Based on severity of AE administer corticosteroids 	
 Ensure adequate evaluation to confirm etiology or exclude other causes
	Grade 3	Withhold or discontinue based on the event ^e		
	Recurrent Grade 3 or Grade 4	Permanently discontinue		

AE(s)=adverse event(s); ALT= alanine aminotransferase; AST=aspartate aminotransferase; CTCAE=Common Terminology Criteria for Adverse Events; DRESS=Drug Rash with Eosinophilia and Systemic Symptom; GI=gastrointestinal; IO=immuno-oncology; ir=immune related; IV=intravenous; SJS=Stevens-Johnson Syndrome; T1DM=type 1 diabetes mellitus; TEN=Toxic Epidermal Necrolysis; ULN=upper limit of normal.
 
Note: Non-irAE will be managed as appropriate, following clinical practice recommendations.
				

irAEs	Toxicity Grade (CTCAE v5.0)	Action With Pembrolizumab	Corticosteroid and/or Other Therapies	Monitoring and Follow-up

^a AST/ALT: >3.0 to 5.0 x ULN if baseline normal; >3.0 to 5.0 x baseline, if baseline abnormal; bilirubin: >1.5 to 3.0 x ULN if baseline normal; >1.5 to 3.0 x baseline if baseline abnormal
 
^b AST/ALT: >5.0 to 20.0 x ULN, if baseline normal; >5.0 to 20.0 x baseline, if baseline abnormal; bilirubin: >3.0 to 10.0 x ULN if baseline normal; >3.0 to 10.0 x baseline if baseline abnormal
 
^c AST/ALT: >20.0 x ULN, if baseline normal; >20.0 x baseline, if baseline abnormal; bilirubin: >10.0 x ULN if baseline normal; >10.0 x baseline if baseline abnormal
 
^d The decision to withhold or permanently discontinue pembrolizumab is at the discretion of the investigator or treating physician. If control achieved or ≤ Grade 2, pembrolizumab may be resumed.
 
^e Events that require discontinuation include, but are not limited to: encephalitis and other clinically important irAEs.
				

LCCC 1729
PI: [name].

5.3.3 Combined Entinostat and Pembrolizumab Dosing Guidelines

In the ongoing study of concurrent pembrolizumab – entinostat administration in patients with solid tumors, no overlapping toxicities have been identified between these two drugs except for the following: fatigue, arthralgia, AST/ALT elevation, rash, and diarrhea. Overall, the treatment regimen has been tolerated well¹⁰⁴.

- If any AEs with grade ≥ 3 are equally attributed to both pembrolizumab and entinostat, reduce entinostat and pembrolizumab as per dosing guidelines in sections 5.3.1 and 5.3.2.
- As with any new treatment, we will also monitor for any AEs that have not been observed with this combination (unexpected SARs will be reported per guidelines) under study.
- If pembrolizumab is permanently discontinued, then entinostat must also be discontinued.

5.4 Concomitant Medications/Treatments/Supportive Care Allowed

All treatments that the investigator considers necessary for a subject's welfare may be administered at his/her discretion, in keeping with the community standards of medical care. All concomitant medications will be recorded on the case report form (CRF) including all prescriptions, over-the-counter (OTC), non-exclusionary herbal supplements, IV medications and IV fluids. If changes occur during the trial period, documentation of drug dosage, frequency, route, and date may also be included on the CRF.

All concomitant medications received within 28 days before the first dose of trial treatment and 30 days after the last dose of trial treatment should be recorded.

